13.4. National Eye Institute Visual Function Questionnaire-25 (NEI-VFQ-25)

The NEI-VFQ-25 consists of a base set of 25 vision-targeted questions representing 11 vision-related constructs, plus an additional single-item general health rating question [Mangione, 2001]. The NEIVFQ-25 generates the following vision-targeted sub-scales: global vision rating, difficulty with near vision activities; difficulty with distance vision activities; limitations in social functioning due to vision; role limitations due to vision; dependency on others due to vision; mental health symptoms due to vision; driving difficulties; limitations with peripheral vision, limitations with color vision; and corneal

pain. Details of deriving domain scores and overall composite score can be found in Section 15.11.3.

For overall composite score and each of 11 sub-scale scores, the descriptive summary of the actual value and change from baseline by visit will be provided.

In addition, summary of worst change from baseline in overall composite score by worst grade of corneal event per GSK scale (0 vs 1-2, vs 3-4) will also be provided. The summary will be based on pooled data of frozen liquid cohort (2.5 and 3.4 mg/kg) and Lyo cohort (3.4 mg/kg).

13.5. Ocular Surface Disease Index

The Ocular Surface Disease Index (OSDI) is a 12-item questionnaire designed to assess both the frequency of dry eye symptoms and their impact on vision-related functioning [Schiffman, 2000].

For the OSDI, the total score will be calculated as well as scores for the three subscales (ocular symptom: item 1-3; visual related function: item 4-9; and environmental triggers: item 10-12).

The total OSDI score = $([\text{sum of scores for all questions answered} \times 100]/[\text{total number of questions answered} \times 4])$. Subscale scores are computed similarly with only the questions from each subscale used to generate its own score. A score of 100 corresponds to complete disability (a response of “all of the time” to all questions answered), while a score of 0 corresponds to no disability (a response of “none of the time” to all questions answered). Therefore, decrease in score from baseline means improvement.

For total score and each of the three sub-scales, the descriptive summary of the actual value and change from baseline by time will be provided.

In addition, summary of worst change from baseline in total score by worst grade of corneal event per GSK scale (0 vs 1-2, vs 3-4) will also be provided. The summary will be based on pooled data of frozen liquid cohort (2.5 and 3.4 mg/kg) and Lyo cohort (3.4 mg/kg).

15. APPENDICES

15.1. Appendix 1: Protocol Deviation Management and Definitions for Per Protocol Population

15.1.1. Exclusions from Per Protocol Population

No per protocol population was defined for the study.

15.2. Appendix 2: Schedule of Activities

15.2.1. Protocol Defined Schedule of Events

Refers to Section 1.2 of Protocol (Version: GSK Document Number [TMF-13990464](#)).

15.3. Appendix 3: Assessment Windows

15.3.1. Definitions of Assessment Windows for Analyses

Not applied to the study.

15.4. Appendix 4: Study Phases and Treatment Emergent Adverse Events

15.4.1. Study Phases

Assessments and events will be classified according to the date/time of occurrence relative to date/time of first dose of study treatment.

Study Phase	Definition
Pre-Treatment	Date/time \leq Study Treatment Start Date/time
On-Treatment	Study Treatment Start Date/time $<$ Date/time

For assessment or event on the first dosing day, whether it is Pre-Treatment or On-Treatment should be based on time if available. If time is not available, the first dosing day (Day 1) is considered Pre-Treatment for ECOG, ECG, vital signs, liver events, lab tests, cardiac scan, and other safety domains, and On-Treatment for adverse events and concomitant medications.

Concomitant Medication and Blood and Blood Supportive Care Product start and end dates will be assigned to study time periods in relation to first dose of study treatment as defined below. The start date references time flag variables and end date reference time flag variables will be added to the concomitant medications and blood and blood supportive products datasets, respectively.

- **Start relative to treatment:** Assign to 'BEFORE' if start date is prior to study treatment start date or if subject has not taken any study treatment or (start date is missing and end date is before study treatment start date). Else assign to 'DURING' if the start date falls into the on-treatment period as defined above or if subject is ongoing (not all study treatment discontinuation records completed) or start date is missing. Else assign to 'AFTER' if start date is after the on-treatment period.
- **End relative to treatment:** Assign to 'BEFORE' if end date is prior to study treatment start date or if subject has not taken any study treatment. Else assign to 'DURING' if start date falls into the on-treatment period or if subject is ongoing (not all study treatment discontinuation records completed) or (end date is missing and start relative to treatment not 'AFTER'). Else assign to 'AFTER' if start date is after the on-treatment period or (end date is missing and start relative to treatment='AFTER').

Only on-treatment blood and blood supportive care products that start after the start of study treatment are included in the Blood Products and Blood Supportive Care Product summaries. Therefore, for summary tables, include blood and blood supportive care product records where start relative to treatment in ('DURING') and end relative to treatment in ('DURING','AFTER'). All data will be reported in listings.

Concomitant medication starts relative to treatment and end relative to treatment flags are used to select data to include in the Concomitant Medication summaries as follows:

- Summary of Concomitant Medications: This summary will contain medications including those with start date prior to study treatment start date and continue (missing end date or end date after study treatment start date) on therapy. Note that any medications with start date and end date prior to study treatment start date will be excluded. In addition, any medication that was started during post-therapy will be excluded. Include concomitant medication records where start relative to treatment in ('BEFORE','DURING') and end relative to treatment in ('DURING','AFTER').
- Summary of Concomitant Medications with On-Therapy Onset: This summary will contain medications with start date after study treatment start date. In addition, any medication that was started during post-therapy (see above for definition of post-therapy) will be excluded. Include concomitant medication records where start relative to treatment in ('DURING') and end relative to treatment in ('DURING','AFTER').

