6.6. Concomitant Medications

Concomitant medications will be coded using GSK Drug coding dictionary, summarized, and listed. The summary of concomitant medications will show the number and percentage of subjects taking concomitant medications by Ingredient. Multi-ingredient products will be summarized by their separate ingredients rather than as a combination of ingredients. Anatomical Therapeutic Chemical (ATC) classification Level 1 (Body System) information will be included in the dataset created but will not appear on the listing or summary.

In the summary of concomitant medications, each subject is counted once within each unique ingredient. For example, if a subject takes Amoxicillin on two separate occasions, the subject is counted only once under the ingredient "Amoxicillin". In the summary of concomitant medications, the ingredients will be summarized by the base only, using CMBASECD and CMBASE. Note: In order to be considered a concomitant medication, the concomitant medication must have been taken at some point during the on-treatment window.

Prophylactic medication for infusion-related reactions and prophylactic topical eye medications will be summarized by drug class and drug name and listed separately. In addition, the percentage of duration of exposure (see Section 15.6.2 for definition) that was on prophylactic steroid eye drop use will also be summarized.

Blood products or blood supportive care products with onset date within the on-treatment window will be included in the summary tables. The frequency and percentage of subjects using blood products and blood supportive care products after the start of study medication will be provided. Supporting listings will also be provided.

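### The end-of-medication flag in SAP 15.4.1 tests the start date, so some medications taken on treatment get no flag and drop out of Table 1.0210 once the subject has discontinued

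*SAP*

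**What the plan says.** SAP Section 15.4.1 defines a start flag and an end flag for concomitant medications and blood products. The end flag is assigned in three steps:

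- BEFORE: "Assign to 'BEFORE' if end date is prior to study treatment start date or if subject has not taken any study treatment".
- DURING: "if start date falls into the on-treatment period or if subject is ongoing". A further alternative covers the case where "end date is missing and start relative to treatment not 'AFTER".
- AFTER: "Else assign to 'AFTER' if start date is after the on-treatment period or (end date is missing and start relative to treatment='AFTER".

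The same section then makes the flags the selection rule for the Summary of Concomitant Medications. The rule opens "Include concomitant medication records where start relative to treatment in" BEFORE or DURING, and also requires an end flag of DURING or AFTER.

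The intended content is stated in three places:

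- Section 15.4.1: "This summary will contain medications including those with start date prior to study treatment start date and continue", where continuing means that the end date is missing or falls after the start of study treatment.
- Section 6.6: to count as concomitant, "the concomitant medication must have been taken at some point during the on-treatment window".
- Section 15.13.4, programming note for Table 1.0210: medications taken on treatment are included, also when they began earlier. The table is a deliverable at the interim, primary and end-of-study analyses.

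**The concern.** A flag that says when a medication ended has to test its end date. Here only the BEFORE step does so. The DURING and AFTER steps test the start date, which the start flag has already used. A medication that began before first dose and ended later can therefore match no step. Because the end flag also selects records, an unassigned flag removes the record from the table.

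At stake is whether Table 1.0210 shows what it says it shows. The medications at risk include those that subjects brought into the trial and stopped during it. The loss also depends on whether the subject is still on treatment, so the content of the table could change between analyses with no change in the medication dates.

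**Working it through.** No sample size, power or error rate is involved, and the plan gives no figure to reproduce. The check applies the flag and selection rules as written to each pattern of start and end date.

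**One record traced.** First dose is day 1. A medication starts on day -30 and ends on day 50. The subject has discontinued and the discontinuation records are complete.

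1. Start flag: the start precedes first dose, so BEFORE. The selection rule accepts this.
2. End flag, BEFORE step: day 50 is not before day 1, and the subject was treated. Not met.
3. End flag, DURING step: the start (day -30) is not in the on-treatment period, the subject is not ongoing, and the end date is not missing. Not met.
4. End flag, AFTER step: the start is not after the on-treatment period, and the end date is not missing. Not met.
5. The end flag is unassigned. The selection rule needs DURING or AFTER, so the record is excluded.

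**All relevant patterns.** The Section 15.4.1 table gives the on-treatment period no upper bound. The patterns were therefore run with an open-ended period and with an assumed end at day 200. Where the two differ, both are shown as open / bounded.

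| Subject | Start | End | Start flag | End flag as written | Kept? | End flag if end date is tested | Kept? |
|---|---|---|---|---|---|---|---|
| Discontinued | day -30 | day -5 | BEFORE | BEFORE | no | BEFORE | no |
| Discontinued | day -30 | day 50 | BEFORE | none | **no** | DURING | yes |
| Discontinued | day -30 | day 300 | BEFORE | none | **no** | DURING / AFTER | yes |
| Discontinued | missing | day 50 | DURING | none | **no** | DURING | yes |
| Discontinued | day -30 | missing | BEFORE | DURING | yes | DURING | yes |
| Discontinued | day 20 | day 50 | DURING | DURING | yes | DURING | yes |
| Discontinued | day 20 | day 300 | DURING | DURING | yes | DURING / AFTER | yes |
| Ongoing | day -30 | day 50 | BEFORE | DURING | yes | DURING | yes |
| Ongoing | missing | day 50 | DURING | DURING | yes | DURING | yes |

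The three bold rows are lost under either period. Testing the end date restores all three and still excludes the medication that both began and ended before first dose.

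**Change over time.** The second row and the first ongoing row are the same record. It is kept while the subject is ongoing and dropped once the discontinuation records are complete.

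**Blood products (Tables 1.0340 and 1.0350).** These require a start flag of DURING, so pre-dose starts never enter them. Of the lost patterns, only a missing start with a known end date after first dose can affect them.

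**The AFTER step.** With no upper bound, no date can fall after the on-treatment period. A medication started on day 250 in a discontinued subject then gets DURING on both flags and is kept, although Section 15.4.1 excludes post-therapy starts. With the period ended at day 200 it gets AFTER and is excluded. The section refers back to a definition of post-therapy that it does not contain.

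**The case against.** The strongest reply is that this is a wording slip carried over from the start-flag bullet. The intended content is stated correctly in the same section, in Section 6.6 and in the note for Table 1.0210, and that note points programmers to a version already produced at the interim. Whether any program applied the rule literally cannot be seen. That stands: the loss is conditional on literal implementation. It does not remove the point, because the wrong date appears in two clauses and Section 15.4.1 makes the resulting flags the selection rule.

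It also stands that the harm is limited. The table is descriptive, and the listing of concomitant medications (Listing 1.0100) is planned with no stated flag filter. That listing is scheduled for the primary analysis only, however, so it would not show records that drop out by the end of study.

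A reader might infer more than the SAP supports:

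- *All pre-existing medications are lost.* They are not. Subjects still ongoing are caught by the ongoing clause, and records with a missing end date are kept.
- *A given share of the table is lost.* The SAP gives no count of such records, so any percentage would be a guess. Section 6.6 counts a subject once per ingredient, so a subject with another qualifying record of that ingredient is still counted.
- *Labelling a medication begun on treatment and ended afterwards as DURING distorts the table.* It changes nothing, because the selection rules accept DURING and AFTER alike.
- *The blood-product tables are broadly wrong.* Only the narrow missing-start pattern reaches them.

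**Conclusion.** The point holds within stated limits. As written, the end-flag rule leaves a record unflagged, and so outside Table 1.0210, when three conditions meet: the subject's treatment discontinuation records are complete; the medication began before first dose or has a missing start date; and its end date is known and falls after first dose. For pre-dose starts this directly contradicts the content stated in Section 15.4.1; for any such medication taken on treatment it contradicts Section 6.6.

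Every record of this kind is lost under a literal reading. The number cannot be derived from the SAP and does not translate one-for-one into table counts. The loss can only grow as more subjects complete discontinuation, so it bears most on the later deliveries of the table.

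The conclusion assumes that the rule is programmed as worded. Missing is taken to mean wholly missing, since Section 15.7.2.1 imputes partial medication dates. The result does not depend on where the on-treatment period ends. These flags select medication and blood-product records for descriptive tables; no efficacy endpoint or test rests on them. The correction should be made, but it is not critical.

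**What to change.** In the end-flag bullet of Section 15.4.1, replace the start date with the end date in the first condition of both the DURING and the AFTER clause. Leave the ongoing and missing-end-date conditions as they are.

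In the same section, state when the on-treatment period ends, and so what post-therapy means. Without that bound AFTER cannot be assigned on a date. The change of date alone is enough to restore the dropped records.

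Then re-derive the flags for Table 1.0210. For Tables 1.0340 and 1.0350, check the records in discontinued subjects with a missing start date and a known end date after first dose.

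The cost is a short text correction and one re-derived flag. No new data are needed. If the existing program already tests the end date, only the text changes.

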15.4.2. Treatment Emergent Flag for Adverse Events

Flag	Definition
Treatment Emergent	
• Study Treatment Start Date \leq AE Start Date• AE Start Date is missing

NOTES:

- If the study treatment stop date is missing, then the AE will be considered to be On-Treatment.
- Time of study treatment dosing and start/stop time of AEs should be considered, if collected.

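### The on-treatment phase in SAP 15.4.1 has no end, so the AFTER flag and the post-therapy exclusion for medications and blood products cannot work

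*SAP*

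**What the plan says.** SAP section 15.4.1 opens with "Assessments and events will be classified according to the date/time of occurrence relative to date/time of first dose of study treatment". Its phase table has two rows. Pre-Treatment is at or before the start of study treatment. On-Treatment is "Study Treatment Start Date/time $<$ Date/time". There is no third row, and the last dose is not mentioned.

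The same section then builds on a bounded period:

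- Start flag for medications and blood products: "Else assign to 'AFTER' if start date is after the on-treatment period".
- End flag: DURING and AFTER are again decided by where the start date falls. The end date enters only for BEFORE and where it is missing.
- Both concomitant-medication summaries drop medication begun in post-therapy. The second adds "any medication that was started during post-therapy (see above for definition of post-therapy) will be excluded".
- Blood-product summaries keep only records whose start flag is DURING.

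Section 6.6 uses the same window as its inclusion test. A concomitant medication must have been taken at some point within it, and "Blood products or blood supportive care products with onset date within the on-treatment window will be included in the summary tables".

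For adverse events, section 15.4.2 calls an event treatment-emergent if it starts on or after treatment start, or if its start date is missing. A note adds: "If the study treatment stop date is missing, then the AE will be considered to be On-Treatment".

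The SAP does define an end of exposure elsewhere. Section 15.6.2 ends exposure at the earlier of last infusion + 20 days and death. A footnote to mock shell SAFE_T21 in Appendix 14 puts the end of treatment exposure at last infusion + 20 days. Neither is linked to the phases or flags.

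**The concern.** The flag rules and the exclusions need three periods, and the phase table supplies two. A programmer has two choices. One is to follow the text, in which case AFTER never occurs and the exclusion does nothing. The other is to pick an unstated cut-off, in which case the result cannot be reproduced from the plan.

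At stake is what the on-treatment tables describe. Table 1.0210 (concomitant medications) is due at the interim, primary and end-of-study analyses, and Tables 1.0340 and 1.0350 (blood products and blood supportive care) at the primary analysis. Under the literal rule they would include anything collected after first dose, however long after the last infusion. The end-flag fault pushes the other way, because it removes medications that the text says are kept.

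**Working it through.** The plan gives no figure to reproduce. The check is one of date logic.

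**1. Can AFTER be reached?** AFTER requires a start date beyond the end of On-Treatment. On-Treatment is every date/time after first dose. No date satisfies both conditions, so start flag AFTER is impossible. End flag AFTER needs the same start-date condition, or start flag AFTER, so it is impossible too.

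**2. Literal application.** Assumptions: first dose on day 1; four infusions 21 days apart, so the last is on day 1 + 3 × 21 = 64; treatment discontinued. Start days are missing or each day from −30 to 730. End days are missing or every tenth day from −30 to 730. No end precedes its start. This gives 30,176 combinations.

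| End of on-treatment | Start BEFORE | Start DURING | Start AFTER |
|---|---|---|---|
| None (as written) | 2,362 | 27,814 | 0 |
| Last infusion + 20 = day 84 (illustration) | 2,362 | 5,978 | 21,836 |
| Last infusion + 30 = day 94 (illustration) | 2,362 | 6,634 | 21,180 |

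As written, starts on days 70, 95, 200 and 400 are all DURING. With either illustrative end, day 70 stays DURING and days 95, 200 and 400 become AFTER. The counts describe the grid, not expected patient records.

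**3. The end flag.** Take a discontinued subject and a medication begun before first dose, with a known end after it.

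- BEFORE fails, because the end is not before first dose.
- DURING fails, because the start is not on-treatment, the subject is not ongoing and the end is not missing.
- AFTER fails, because the start is not after the period.

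The record gets no end flag. The summary selects end flags DURING or AFTER, so the record is lost, although the same bullet says that medication begun earlier and continuing past treatment start is included. A missing start with a known end after first dose fails in the same way.

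On the grid, 31 early start days (−30 to 0) plus one missing start, times 73 end days after first dose, gives 32 × 73 = 2,336 unflagged combinations. The number is the same in all three rows of the table, so giving the period an end does not cure this fault.

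**4. Was an open window meant for these flags?** The start rule has a separate clause making records DURING when the subject is still on treatment. With an open-ended period that clause would be needless for any start after first dose. It makes sense only if the period was meant to close after discontinuation.

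**The case against.** **Adverse events.** A reader might infer that the treatment-emergent flag is wrong in the same way, and that toxicity from a later line of therapy is credited to study drug. The document does not support this. Section 15.4.2 is a complete rule with no unreachable category. How late events are collected is normally a protocol matter, and the protocol is not shown. The SAP also studies late ocular events on purpose: SAFE_T21 counts events with onset after exposure, and section 8.5 follows findings from end of treatment to last follow-up. Relatedness comes from the investigator (section 8.1, with missing counted as related), not from this flag. What remains is a note about a stop date that the flag does not use.

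**Size.** It is tempting to divide the length of survival follow-up by the length of exposure and call the ratio the inflation. That compares assumed window lengths, not records. Nothing in the SAP shows that medications or transfusions are collected throughout survival follow-up.

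**Blood products.** Section 6.6 also speaks of use after the start of study medication, which fits an open window. But the same paragraph restricts the tables to the on-treatment window, and section 15.4.1 keeps only DURING starts. The wording conflicts, so the open reading is not established.

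**Reach.** No efficacy result is touched. Section 7.1.1 cuts response assessments at confirmed progression or new anti-cancer therapy, and PFS has its own censoring rules in section 7.2.1.5. This stands, and it limits the weight of the point.

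**Conclusion.** The point holds for the medication and blood-product flags. This is more than missing detail: the stated rules give a result that contradicts their stated purpose. The post-therapy exclusion removes no record, AFTER cannot occur, and some medications that the text includes are dropped in discontinued subjects.

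The effect is on descriptive tables only. How many records change depends on the collection window. If collection stops soon after the last infusion, few late records exist and the first fault matters little in practice. The end-flag fault does not depend on late collection. It arises for any discontinued subject with such a medication.

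For adverse events the finding is limited to a mismatch between the treatment-emergent rule and its note.

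**What to change.** In SAP section 15.4.1:

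- State an end for the on-treatment period used by the medication and blood-product flags. Tie it to the last infusion, and make it consistent with the protocol's collection window and with the SAP's own end-of-exposure definition (last infusion + 20 days). The sponsor sets the length.
- Define post-therapy as anything later.
- Base the end flag on the end date: DURING if it falls within the period, AFTER if it falls later. Keep the existing provisions for missing ends and ongoing subjects. The present selection filter then returns what the text describes.

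In section 6.6, make the blood-product sentences refer to the same window.

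In section 15.4.2, only reconcile the text. Either say that the treatment-emergent flag is deliberately open-ended and delete the stop-date note, or align the flag with the protocol's adverse-event window. A cap at new anti-cancer therapy is a design choice and is not asked for here.

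The cost is a few lines of wording and re-derived flags. One caution: sections 9 and 12.2 show that primary-analysis work is already done. Table 1.0210 at end of study may then not match its primary version and needs a footnote. Tables 1.0340 and 1.0350 change only if they are rerun.
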